E.1.1. Potential Risks. With regards to completing study measures, there is a risk of discomfort or distress in answering questions. However, distress and discomfort related to questionnaire completion and the psychiatric interview are usually temporary and well-tolerated. Participants are informed that they may refuse to answer any questions while completing the questionnaires. Risks also include discomfort related to alcohol withdrawal. Symptoms of alcohol withdrawal may include headache, insomnia, sweating, shakiness, and rarely, seizures or hallucinations. We will minimize risk of alcohol withdrawal by screening participants at high risk for withdrawal out of the study. However, in case enrolled patients experience alcohol withdrawal that is not reported at the screening visit, we will instruct patients to report symptoms to research staff. There are risks related to participants providing a blood fingerstick. The risks of having a blood puncture includes temporary pain for the needle stick, bruising, and rarely, infection. Some people may experience dizziness, possibly lightheadedness, or rarely, fainting. Finally, there is a potential risk associated with the loss of confidentiality of study data. Because of these risks, the data and safety monitoring plan (DSMP) for this trial focuses on monitoring by the principal investigator (PI), the study physician, and the study coordinator, along with prompt reporting of unexpected and serious adverse events to NIH and to the Institutional Review Board at DUMC.

E.1.2. Potential Benefits. While participants may benefit from quitting or reducing alcohol use, there are no guaranteed benefits to the individual participant and no immediate benefits of the proposed research to others. There are potential benefits to others from the information generated that potentially will be helpful in developing more effective treatment interventions for veterans with AUD.

E.1.3. Protections Against Risk. The study is completely voluntary and participants are informed that they are free to refuse to answer any items on the questionnaires or questions from the interview that they do not wish to answer. They are also informed that they are free to decline participation in any procedure and can withdraw from the study at any time.

Potential risks will be minimized by carefully screening potential participants according to the inclusion/exclusion criteria, closely monitoring symptom levels, and following established laboratory procedures. Finally, all project staff will complete educational units required by DUMC's IRB and Duke Office of Clinical Research.

In accordance with NIH's recently revised guidelines re: Certificates of Confidentiality (CoC), this study will utilize an NIH CoC. Participants will be informed of the COC during the informed consent process.

With regards to data security, potential risks will be minimized in several ways. Subjects' identifying information will only be available to [name] and the research staff at DUMC. Data that links participants to information collected in the course of a given study will be kept separately from identifying information in computerized logbooks maintained at each study site. All study data will be kept in a secured file to which only study investigators will have access. Hard copy paper records will be stored in a locked filing cabinet in the study coordinator's locked offices at Duke-leased space at North Pavilion. Information from the interview and/or questionnaires will be entered into a computerized database. Each password-protected database will be stored on a networked computer on a server that is encrypted, password-protected, and only accessible by [name] and study staff, see duhsnas-pri\dusom_psych\private\irb\[name]\CM CBT. Access to these data will be limited to a small number of project staff who have been trained to preserve participant confidentiality. The key linking code numbers and identifying information will be maintained in a separate database and stored in the same protected computer environment described above.

Video recordings that are made in the laboratory (i.e., recordings of therapy sessions in order to measure treatment fidelity) will be made using a Duke-owned iPad or iPhone. Recordings will be transferred to a Duke secured server immediately after recording. Regarding the mCM portion of the intervention, we have developed several ways to minimize data security risk. The smart phone used will be any one of four models of Droid phones: 1) Droid Turbo 2 (Motorola Mobility Inc, Libertyville, IL) with a Qualcomm Snapdragon 810 processor, 5.4" Quad HD display; 2) Droid Turbo, with 5.2" Quad HD Super AMOLED™ Corning® Gorilla® Glass 3 Display; 3) Droid MAXX, with a dual-core 1.2 Ghz processor, 1 GB DDR2 RAM, and 4.3" gHD display; or 4) Droid MAXX 2 DROID MAXX 2 with an octa-core 1.7 Ghz processor, 2 GB RAM, and 5.5" full HD display. Each will be equipped with an Android operating system that is compliant with Federal Information Processing Standard (FIPS) 140-2 standards. Features other than the electronic diary, calling, and texting features will be locked out. The phone will be programmed so that staff can set up the phone by simply entering a participant's code. Encrypted TLS connections will be used to upload data to the server. The study's website will use a Virtual Private Server provided by InMotion Hosting, Inc. The data at InMotion Hosting are Advanced Encryption Standard (AES)-256 encrypted at rest, and the data being transferred are encrypted at transfer AES-256 & Transport Layer Security (TLS). Website properties include TLS 1.0, AES w/ 128 bit encryption (High); Rivest-Shamir-Adleman (RSA) with 2048 bit exchange. The web application written for this study has been checked for SQL injection, Code Injection, XSS, and RFI vulnerabilities and has passed. The site will only be accessible to staff via 512-bit SHA-2 hashed passwords.

E.1.3. Psychiatric Emergencies. As this study includes a novel therapeutic intervention that is behavioral in nature, we do not anticipate study-related SAEs to occur. It is not unanticipated that participants may endorse suicidal or homicidal ideation. We have developed a homicidal (HI) and suicidal (SI) risk assessment checklist based on the currently available research evidence base. All staff members are trained in the use of the assessment instrument, and attend monthly supervision meetings in which HI/SI assessments are regularly reviewed. Our laboratory has a policy regarding SI and HI risk assessment and follow-up. According to the policy, if a participant is deemed at "high" risk of suicide or homicide, the study staff providing the assessment will contact a senior staff member with clinical training who will provide a second opinion. If the senior staff member determines that the participant is in imminent risk of suicide or homicide, that participant will be escorted to the DUMC or DVAHCS emergency room for evaluation for psychiatric hospitalization. If at any time a participant is deemed by our staff to be at imminent risk of harm to self or others, he/she will be immediately withdrawn from the study upon being escorted to the emergency room. If a participant is deemed to be at "low" or "moderate" risk, the study staff member performing the assessment will discuss treatment options with the participant and discuss psychiatric emergency resources that may be available to him or her. Finally, in the case

of moderate SI or HI, study staff will review the assessment with a senior staff member in order to ensure that follow-up has been adequate.

E.1.4. Participant Referrals. Following the standard of care for AUDs, all participants will be referred to aftercare and encouraged to participate in 12-step programs or outpatient relapse prevention treatment in the Durham VA Health Care System or at DUMC following completion of the 12-session CBT intervention. In addition, appropriate referrals will be completed to address any clinically significant increases in symptoms of comorbid psychiatric or medical problems. Referrals will be made first to treatment at DVAHCS, where participants must be enrolled for primary care services. In the event that treatment is not available at DVAHCS or DUMC, referral will be made to a community provider.

E.2. Data and Safety Monitoring Plan

The individuals responsible for data safety and monitoring will be the principal investigator and the project manager. The study physician, [name]., Ph.D., will serve as a Medical Monitor and in that role, provide additional safety monitoring regarding diagnostic and medical issues in enrollment decisions and any medical questions that arise during treatment. [name] is a board-certified psychiatrist with 18 years of experience providing pharmacotherapy in clinical research studies and clinics. He is also a psychiatrist in the Durham VA Health Care System, where he serves as a clinician treating substance use disorders. He has collaborated on research with our group over the past 10 years. [name] has expertise in AUDs and has current and past grant funding from NIH and VA for alcohol-related research. Further data safety and monitoring will be provided by the PI.

As study physician and medical monitor, [name] will ensure participants are medically cleared to participate in this trial and will review all reports of adverse events sent by the study coordinator and evaluate the patient as necessary to determine whether there is any corrective action needed. The Principal Investigator (PI) will be responsible for executing the DSMP, and complying with reporting requirements.

Further data safety and monitoring will be provided by the PI. There will be several ongoing mechanisms for monitoring and reporting of AEs, including SAEs: 1) ongoing participant contact via study personnel; 2) a telephone number provided to participants to report concerns related to study participation; and 3) weekly meetings between the PIs and study personnel. Any adverse events (AEs) will be reported to the IRB in accordance with the Duke University School of Medicine's Human Research Protection Program.

In order to monitor possible negative effects with regards to treatment, including alcohol withdrawal symptoms, participants will be instructed to report any negative effects as soon as possible to research staff; they will have contact information needed to report these problems to study personnel.

The PI will meet at least weekly with study personnel to discuss participants' reactions to the intervention, proper delivery of the intervention, and any adverse events or unanticipated problems. Monthly meetings between the investigators and the project manager will allow for ongoing progress reports, including the number of participants currently involved in the study groups, attrition rates, and scheduled data collection from participants, as well as notification and review of any AEs. Safety monitoring for adverse events will be conducted in real time by the PI and/or project manager. The following information about adverse events will be collected: 1) the onset and resolution of the AE, 2) an assessment of the severity or intensity, 3) an assessment of the relationship of the event to the study (definitely, probably, possibly or not related), and 4) action taken (e.g., none, referral to physician, start or increase concomitant medication). The PI will determine the severity of the event, will assign attribution to the event, and will monitor the event until its resolution.

F. STATISTICAL ANALYSES AND POWER CONSIDERATIONS

Variables of interest will be examined using means, standard deviations, and distributions (for continuous variables) and their frequencies (for categorical variables). For normally distributed outcome variables, linear statistical models will be used by default. However, examination of residuals and Q-Q plots will be undertaken to determine whether generalized linear modeling may be more appropriate. We will first conduct preliminary analyses to ensure that there are no differences across treatment groups with respect to gender, age, educational history, socioeconomic status, baseline alcohol consumption, PTSD symptoms, and depressive symptoms. In addition, we will evaluate potential effects of psychiatric variables on the treatment response. We do not expect differences to arise on these measures as a result of randomization. Nevertheless, we will potentially use covariate adjustment to address unanticipated differences in baseline variables. We will conduct sensitivity analyses to determine how variability in demographic/baseline variables influence estimates of treatment effects (Thabane et al., 2013).

We plan to ask participants to report both gender and biological sex so that we can evaluate the role of biological sex on study outcomes. The association between sex and outcomes will be evaluated for all three aims. We will conduct sensitivity analyses to determine how variability in demographic/baseline variables influence estimates of treatment effects by analyzing and reporting the effects of randomization on males and females separately.

Multilevel modeling (MLM) will be used to analyze primary treatment outcomes (i.e., number of heavy drinking days; abstinence outcomes). MLM is appropriate for analyzing repeated-measures data; however, unlike ANOVA, MLM can accommodate data missing at random (Searle, Casella, & McCulloch, 1992). Because MLM takes into account the shared variance among observations within a given person, it can be used to leverage repeated measurements of alcohol use to enhance statistical power.

Although we do not anticipate much missing baseline data, we do anticipate missing values at post-treatment and each of the 6- and 12-month follow-ups due to attrition. Given evidence that maximum likelihood (ML) and multiple imputation (MI) provide the least biased results in comparison to last observation carried forward and worst-case scenario (i.e., missing=relapsed) in alcohol clinical trials under varying missing data assumptions (Hallgren & Witkiewitz, 2013), both approaches will be used here. MLM uses ML estimation; thus, missing values result in casewise—but not listwise—deletion. Consequently, participants with missing data will still be included in the analyses; estimates based on them will simply have a greater level of uncertainty. MI will be used to impute missing data using baseline demographic, clinical, and drinking measures. Regression parameter estimates will be computed for each imputation dataset and then pooled using Rubin's rules (Rubin, 1976). Sensitivity analyses will be conducted to determine how modeled treatment effects may vary by missing-data approach.

Aim 1: To examine the first hypothesis that CM will be associated with greater treatment engagement and treatment completion than the control condition, treatment engagement will be defined as the number of counseling sessions completed, with treatment completion defined as completion of all 12 counseling sessions. Potential group differences in treatment engagement as a function of counseling sessions completed will be examined using independent *t*-tests. Contingency-table analysis will be used to examine whether a greater proportion of the CM participants complete the treatment in comparison to the control group. The second hypothesis is that CM will be associated with higher rates of self-reported abstinence and fewer heavy drinking days at 6 and 12 months. MLM will be used to model each of these outcomes. Specifically, logistic MLM will be

conducted to model abstinence as a function of treatment, time (categorized as end of treatment, 6 months, 12 months), and the interaction between treatment and time. Randomization to long-term abstinence incentive will be covaried. Linear contrasts will be specified at each time point to examine the hypothesis that CM will result in higher abstinence rates than CBT alone at 6 and 12 months. A similar count-based model (e.g., Poisson, negative binomial) will be conducted to analyze number of days of heavy drinking (per 30 days). In addition to modeling the effects of treatment, time, and the interaction between treatment and time, number of days of heavy drinking recorded at baseline and randomization to the long-term abstinence incentive will be covaried. Again, linear contrasts will be derived at each time point to compare treatment effects at 6 and 12 months.

Aim 2: To examine the hypothesis that mCM paired with CBT for SUD will be more cost effective over the lifetime than CBT alone, cost-effectiveness analysis (CEA) will be performed using the incremental cost-effectiveness ratio (ICER), with costs as the numerator and effectiveness as measured by quality-adjusted life years (QALY) as the denominator. QALYs incorporate changes in quality of life (morbidity) using a set of values, one for each possible health state, reflecting the relative desirability of the health state (Drummond et al., 2009). Quality of life ratings, or utilities, will be derived from a prior study of the utility of different drinking states that used the standard gamble technique in a community/clinic sample of 200 individuals (Kraemer et al., 2005). The mean utility values (and standard deviations) calculated for each state were as follows: abstinent 0.93 (0.15), moderate drinking 0.88 (0.22), at-risk drinking 0.82 (0.27), meeting criteria for mild AUD 0.75 (0.29), meeting criteria for severe AUD 0.67 (0.29), and in recovery from alcohol dependence 0.83 (0.24). QALY change will be calculated based on change from baseline to 12-month drinking status. Prior to CEA, CBT alone will be assessed for dominance to determine whether it is both less costly and more effective than combined mCM and CBT. In the absence of dominance, an incremental cost-effectiveness ratio (ICER) will be computed to estimate the additional cost required to achieve one additional QALY. Specifically, the ICER combines the costs of the treatments with the QALY changes, using the cost in the mCM group over and above the control, divided by the incremental QALYs in the mCM group over and above the control. Given likely skewed economic data, nonparametric bootstrap resampling will be used to test the sensitivity of the calculated ICERs and cost-acceptability curves estimated to assess the probability that the mCM intervention is cost-effective at thresholds up to \$50,000 or \$100,000 per QALY (Willan & Briggs, 2006). Numerous sensitivity analyses will be conducted to evaluate the robustness of these results given varying estimates of abstinence rates, relapse to any heavy drinking, mortality rates, and long-term costs of sustained alcohol use. Cost-effectiveness analysis will be conducted if the primary outcome is significant; otherwise, a cost minimization analysis will be conducted.

Aim 3: To examine the hypothesis that incentivizing long-term abstinence will increase AUD aftercare treatment utilization, enrollment in VA and/or non-VA alcohol treatment programs will be determined both in the first 6 months following randomization and the second 6 months leading up to the 12-month follow-up. Logistic MLM will be used to model treatment utilization during each of these intervals as a function of randomization to the long-term abstinence incentive, time, and the interaction between group and time. Randomization to CM will be covaried. Linear contrasts will be specified at each time point to examine the hypothesis that long-term incentives to promote abstinence will result in greater likelihood of AUD treatment utilization both prior to and following the 6-month incentive. To examine the hypothesis that long-term abstinence incentives will be associated with higher rates of self-reported abstinence and fewer heavy drinking days at 6 and 12 months, MLM analyses similar to those proposed for Aim 1 will be conducted. Specifically, logistic MLM will be used to model abstinence as a function of long-term incentive, time (categorized as end of treatment, 6 months, 12 months), and the interaction between incentive and time. Randomization to CM will be covaried. Linear contrasts will be specified at each time point to examine the hypothesis that a long-term incentive for abstinence will result in higher abstinence rates than no incentive at 6 and 12 months. A similar count-based model (e.g., Poisson, negative binomial) will be conducted to analyze number of days of heavy drinking (per 30

days). In addition to modeling the effects of long-term incentive, time, and the interaction between incentive and time, number of days of heavy drinking recorded at baseline and randomization to CM will be covaried. Linear contrasts will compare effects of the incentive at 6 and 12 months.

Power calculations provided below were performed with Power Analysis and Sample Size software (PASS, Version 12: NCSS LLC, Kaysville, Utah). The sample size estimate is based on the first hypothesis that the CM intervention will result in higher overall self-reported abstinence rates and fewer days of heavy drinking at 6-months post-randomization. As described in the analysis section, this hypothesis will be tested via linear contrasts specified within the context of MLM analyses. Because this will be tested using repeated-measures data, statistical power will depend on the effective sample size (ESS). The ESS is the number of statistically independent observations available for this study, which is equivalent to the total number of observations (number of participants x number of data collections) adjusted for within-individual correlations. As the intraindividual, or intra-class, correlation (ICC) decreases, the ESS increases. Given that we found an ICC of .20 for 7-day point prevalence measured at posttreatment, 3 months, and 6 months in an RCT with 218 smokers featuring CM as the experimental treatment (R01 CA196304), we anticipate a similar, if not smaller, figure in this trial, given longer intervals between observations. Using this ICC value, with 140 participants with up to 3 observations each, the ESS would be 300. Even with an unexpectedly high 15% attrition at each observation point, such that only 119 complete treatment, 101 6-month follow-up, and 86 12-month follow-up, the ESS for examining linear contrasts would be 227, which would be sufficient to detect treatment effects as small as Cohen's $d = 0.43$ with 90% power. Because the previous trial examining the effect of CM as an adjunct to behavioral treatment found large effects (Cohen's $d = 0.92$; McDonell et al., 2017) on heavy drinking days, our proposed sample size has sufficient statistical power.

G. PROJECT MANAGEMENT PLAN and TIMELINE

The scheduled project timeline is illustrated in Table 5. Members of this multi-disciplinary research team have experience in one or more key components of the

Activity	Year 1				Year 2				Year 3				Year 4				Year 5			
	1	2	3	4	1	2	3	4	1	2	3	4	1	2	3	4	1	2	3	4
Hire/Train Staff	■																			
Recruitment		■	■	■	■	■	■	■	■	■	■	■								
Intervention			■	■	■	■	■	■	■	■	■	■								
Follow-ups: post-txt, 6-and 12-months			■	■	■	■	■	■	■	■	■	■		■	■	■	■			
Data Analysis														■	■	■	■	■	■	■

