As shown in Figure 3, proposed is a 2X2 factorial randomized clinical effectiveness trial testing the effects of combining CM as an adjunct to state-of-the-art, evidence-based CBT (CBT + CM vs. CBT only) and the effects of a single, long-term incentive for bioverified abstinence/no heavy drinking at 6-months follow-up (Long Term Incentive vs. No Incentive). All patients will be referred to standard aftercare and encouraged to participate in 12-step programs following the intervention. Use of aftercare and other health care utilization will be collected based on objective measures (VA electronic medical record) and participant report. Health-related quality of life will be collected at each follow-up. The primary endpoint (AIM 1) will be number of heavy drinking days in the past 30 days at the 6-month follow-up. Cost effectiveness analysis (AIM 2) will be performed using quality-adjusted life years (QALY) as the outcome. The utility of a long-term incentive (AIM 3) will be tested by examining use of aftercare and other alcohol-related treatment and heavy drinking days in the past 30 days at the 6 and 12-month follow-ups.

D.2. Patient Identification, Eligibility, and Recruitment

Patients will be identified from the Durham VA Health Care System (DVAHCS) using the hospital's computerized medical record. Records will be screened for AUD. After mailing introductory materials with an opt-out number, we will contact those who do not opt out via telephone to explain the study and recruit them for participation. If necessary, in order to reach female veterans, we can oversample women for the screening mailouts.

Figure 3. Trial Design

We will also utilize reactive recruitment methods as needed to reach potentially eligible veterans. For example, we will seek referrals from the DVAHCS Substance Use Disorders Clinic. In order to reach female veterans, we will seek referrals from the Women's Health Clinic. In addition, we will post IRB-approved flyers and brochures throughout the DVAHCS catchment area, especially in clinic areas and Vet Centers. In addition, we will post, if necessary, flyers and brochures in the community, in local restaurants, laundromats, university student centers, etc. We will also use online classified advertisements such as Craigslist.com to reach potential participants.

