Potential participants who discuss the study with study personnel will complete a brief phone screen to assess potential eligibility. Veterans who are potentially eligible will attend a screening session where they will complete diagnostic interviews, self-report measures, urine drug screen and alcohol breathalyzer to determine inclusion. Participants who screen in will be randomized at the first treatment session to one of two treatment conditions (CBT+mCM vs. CBT alone) and to one of two long term incentive conditions (abstinence incentive at 6 months vs. No incentive). Stratified permuted block randomization assignments will be performed using a computerized sequence generated by the study statistician before the study starts. The sequence will be password-protected so that only the statistician and other study staff who do not have patient contact will have access to the sequence. We will stratify on the presence of comorbid non-tobacco SUD.

D.4. Interventions

D.4.1. Cognitive-Behavioral Therapy for Substance Use Disorders

We will use the VA CBT for SUD protocol (DeMarce, Gnys, Raffa, & Karlin, 2014) to provide in-person treatment in both study arms. CBT will be provided by a therapist with at least a Master's degree in mental health (e.g., psychology, social work) who has reviewed CBT for SUD training materials. To prevent confounding from therapist effects, study therapists will treat cases in both study arms. CBT sessions will be weekly over 12 weeks as shown in Figure 3. Following the standard of care for AUDs, all participants will be referred to aftercare and encouraged to participate in 12-step programs following completion of the 12-session CBT intervention (Proctor & Herschman, 2014).

Figure 3. Timeline for Intervention and Follow-Ups

D.4.2. Mobile Contingency Management for AUD Procedures

As shown in Figure 3, participants will begin one week of practice mCM monitoring at session two of CBT so they can troubleshoot any difficulties they have using the app. The beginning of contingent reinforcement (i.e., the target quit date) is scheduled for the same date as session three of CBT (week 3), which will provide eight weeks of mCM before the end of CBT. Patients who attend all weekly appointments will have two sessions of CBT occurring after mCM ends to assist in preventing relapse when monetary reinforcement is removed.

Table 2. Virtual Scratch-Off Lottery Ticket Reinforcement Amounts				

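### The randomisation stratum is in no Aim 1 or Aim 3 analysis and the abstinence models omit baseline drinking, which forgoes a modest amount of power, mainly for abstinence

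*Combined protocol and SAP*

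**What the plan says.** Section D.3 describes stratified permuted-block randomisation with one stratification factor: "We will stratify on the presence of comorbid non-tobacco SUD".

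Section D.1 sets the primary endpoint: "The primary endpoint (AIM 1) will be number of heavy drinking days in the past 30 days at the 6-month follow-up". Section F then specifies the analyses.

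- **Aim 1, heavy drinking days.** A count model with treatment, time and their interaction. For covariates, "number of days of heavy drinking recorded at baseline and randomization to the long-term abstinence incentive will be covaried".
- **Aim 1, abstinence.** A logistic multilevel model, to "model abstinence as a function of treatment, time (categorized as end of treatment, 6 months, 12 months), and the interaction between treatment and time". The only covariate is the other randomised factor: "Randomization to long-term abstinence incentive will be covaried".
- **Aim 1, engagement and completion.** A t-test on session count, and for completion, "Contingency-table analysis will be used to examine whether a greater proportion of the CM participants complete the treatment".
- **Aim 3.** The same pattern: "logistic MLM will be used to model abstinence as a function of long-term incentive, time" and the interaction, with CM assignment as the only covariate. The heavy-drinking-day model adds its baseline value. The treatment-utilisation model has neither the stratum nor baseline drinking.

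The opening of Section F says the arms will be compared on several baseline variables, including alcohol consumption, and that adjustment may be used if unexpected differences are found. Comorbid SUD is not among the variables listed. Baseline drinking also enters the multiple-imputation model.

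**The concern.** A factor important enough to stratify on is normally carried into the analysis. Stratification balances the arms on it, and a model that ignores it takes no credit for that balance. The second gap is an inconsistency: within each aim, one alcohol outcome is adjusted for baseline drinking and the other is not, with no reason given.

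Abstinence is not a side issue here. Section F groups it with heavy drinking days as a primary treatment outcome, and the sample-size paragraph rests on both. In a logistic model, leaving out a prognostic covariate moves the treatment odds ratio toward 1 relative to the conditional one, and power falls.

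The fallback in Section F does not close the gap. It commits to nothing and makes the model depend on what the data show. Stratification also makes imbalance on the stratum unlikely, so the trigger would seldom bring the stratum in. The benefit of adjustment comes from a covariate being prognostic, whether or not it is imbalanced.

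**Working it through.** **1. The plan's own power figure.** Inputs from the power paragraph of Section F: 140 participants, 3 observations each, intra-class correlation 0.20, and 119, 101 and 86 remaining at the three time points. Alpha and sidedness are not stated; two-sided 0.05 and 1:1 allocation are assumed.

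- No attrition: 140 × 3 / (1 + 2 × 0.20) = 420 / 1.4 = 300.
- With attrition, 86 people have 3 observations, 101 − 86 = 15 have 2, and 119 − 101 = 18 have 1. Summing m / (1 + (m − 1) × 0.20) over people: 86 × 3/1.4 + 15 × 2/1.2 + 18 = 184.3 + 25 + 18 = 227.3.
- Detectable effect at 90% power: (1.960 + 1.282) × √(2/113.5) = 0.43.

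All three figures reproduce, and none assumes covariate adjustment. The omission therefore does not make the stated power wrong.

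**2. The stratum alone.** The documents give neither its prevalence nor its prognostic strength. Assume prevalence 0.35 and a standardised outcome difference of 0.2 to 0.5 between strata. With v = 0.35 × 0.65 × difference², R² = v/(1 + v):

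- difference 0.2: v = 0.0091, R² = 0.009
- difference 0.5: v = 0.0569, R² = 0.054

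Put residual SD = √(1 − R²) into a two-sample power calculation at d = 0.43. This is a linear approximation.

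| Sample size | No adjustment | R² 0.01 | R² 0.05 |
|---|---|---|---|
| 227 (effective) | 0.900 | 0.902 | 0.914 |
| 101 | 0.580 | 0.584 | 0.601 |

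The gain is about 0 to 2 points. The primary model already holds baseline heavy drinking days, so this is roughly all that it forgoes.

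**3. Both covariates in the abstinence analysis.** Single-time-point logistic simulation, 3,000 replicates per row, blocks of 4 within stratum. Assumed: n = 101, abstinence 30% v 55%, stratum prevalence 0.35. Coefficients are log-odds, per SD for baseline drinking.

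| Baseline drinking | Stratum | Unadjusted | + stratum | + both |
|---|---|---|---|---|
| 0 | 0 | 0.710 | 0.716 | 0.714 |
| 0.4 | 0.4 | 0.709 | 0.716 | 0.736 |
| 0.8 | 0.4 | 0.710 | 0.715 | 0.777 |
| 0.8 | 0.8 | 0.732 | 0.746 | 0.790 |
| 1.2 | 0.8 | 0.720 | 0.733 | 0.827 |

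The gain from both covariates runs from nil to about 11 points. With n = 227 and 30% v 50%, the last row becomes 0.876 to 0.942, a gain of 6.6 points.

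A second simulation fixed the conditional treatment log-odds at 1.0 (n = 101, control abstinence 25%, stratum prevalence 30%). It gave gains of about 2, 4 and 10 points for weak, moderate and strong predictors, and 1 to 2 points for the stratum alone.

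**4. Standard error and type I error.** In the second simulation, with moderate predictors (log-odds 0.6 each), the mean standard error of the treatment log-odds ratio rose on adjustment from 0.439 to 0.471. Power rose because the estimate moved further from zero. With no treatment effect, the unadjusted tests in the first simulation rejected 4.0% to 5.5% of the time.

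**The case against.** The strongest reply is that little is at stake for the primary endpoint, and this stands. Heavy drinking days at 6 months are already adjusted for their own baseline. Section D.6 also calls abstinence a secondary drinking outcome, although Section F groups it with the primary ones.

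Several stronger readings are tempting and are not supported.

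- **That 101 participants are expected at 6 months.** The plan presents this as an unexpectedly high attrition case. Section D.10 cites earlier retention above 80% at 12 months, which would be more than 0.80 × 140 = 112. The multilevel model also draws on all three time points, which the single-time-point simulations do not.
- **That confidence intervals are too wide by 1/√(1 − R²) − 1**, or about 1% to 5% for R² of 0.02 to 0.10. That is a linear-model formula. It fits the session-count t-test at most, not logistic or count models.
- **That the tests are invalid or the stated power is wrong.** Neither follows from the checks above.

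It can also be said that Section F already provides for baseline adjustment, sensitivity analyses on baseline variables, and imputation from baseline drinking. These are relevant, but none makes either covariate a pre-specified term in the main models, and none names the stratum.

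**Conclusion.** Both omissions are confirmed from the text. They are inefficiencies in the specified models, not errors that invalidate a result. The cost falls mainly on the two abstinence models. With the plan's pessimistic 101 participants, adding both covariates is worth about 0 points if they are not prognostic, 2 to 4 if weak to moderate, and about 10 if strong. The stratum alone is worth about 0 to 2 points, and that is the whole of the loss for the primary heavy-drinking-day analysis.

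The omissions themselves are certain; their size is not. Stratum prevalence, abstinence rates and prognostic strength are all assumed, because the documents give none of them. The top of the range needs baseline drinking to be a strong predictor of abstinence. The gain for abstinence is in power and in an estimate that is not pulled toward 1; a narrower interval for the log-odds ratio should not be expected.

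**What to change.** Amend Section F before outcomes are examined by arm.

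1. Include comorbid non-tobacco SUD, as used in the randomisation, as a fixed effect in the Aim 1 and Aim 3 outcome models.
2. Add baseline heavy drinking days, or percent days drinking, to the abstinence models of both aims. Name the chosen variable in advance.
3. State that these terms replace adjustment triggered by observed baseline differences.

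Replacing the session-count t-test and the completion table with regressions on both randomised factors and the stratum is optional.

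The cost is wording only. Table 3 schedules the diagnostic interview, Timeline Follow-Back, heavy drinking days and percent days drinking at screening, so no new data, visits or participants are needed.
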